#### 7.6.5 ECG

Summary statistics will be presented for each ECG parameter (heart rate, PR interval, QRS duration, QT interval, QTcF interval) and the corresponding changes from baseline by visit and time-point, for each study part.

#### 7.6.6 Vital Signs and Physical Measurements

Not applicable.

#### 7.6.7 Physical Examination Findings

Frequency and percentage of participants with an abnormal physical examination will be provided by visit.

#### 7.6.8 Allen's Test

Not applicable.

#### 8 CONVENTIONS

#### 8.1 Decimal Places

Unless otherwise specified, minimum and maximum will be reported to the precision as the data collected, and with one more decimal place for the mean, median, and standard deviation. Data recorded or derived with more than 2 digits after the decimal will be displayed with minimum and maximum rounded to 2 decimal places and mean, median, and standard deviation rounded to 3 decimal places in summary tables, and with all decimal places in listings (or as space allows).

## 8.2 Imputation of Missing Dates for Adverse Events

## 8.2.1 Incomplete Start Date

Missing day and month:

- If the year is the **same** as the year of the first dosing date, then the day and month of the first dosing date will be assigned to the missing fields.
- If the year is **prior to** the year of first dosing date, then December 31 will be assigned to the missing fields.
- If the year is **after** the year of first dosing, then January 1 will be assigned to the missing fields.

Missing day only:

- If the month and year are the **same** as the year and month of first dosing date, then the first dosing date will be assigned to the missing day.
- If either the year of the partial date is **before** the year of the first dosing date or the years of the partial date and the first dosing date are the same but the month of partial date is **before** the month of the first dosing date, then the last day of the month will be assigned to the missing day.
- If either the year of the partial date is **after** the year of the first dosing date or the years of the partial date and the first dose date are the same but the month of partial date is **after** the month of the first dosing date, then the first day of the month will be assigned to the missing day.
- If the stop date is not missing, and the imputed start date is after the stop date, the start date will be imputed by the stop date.

Missing day, month, and year:

No imputation is needed, the corresponding AE will be included as TEAE.

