2 SCHEDULE OF ACTIVITIES

Study assessments and procedures are presented for screening in Table 2-1 and are presented for imaging assessments and procedures in Table 2-2 (Part A), Table 2-3 (Part B), and Table 2-4 (Part C).

Protocol Amendment No.: 05

Table 2-1: Screening Procedural Outline for Parts A, B, and C (IM038010)

Procedure	Screening Visit(s) (Day -30 to Day -1)	Notes
Eligibility Assessments and Related Procedures		
Informed Consent	X	A participant is considered enrolled only when a protocol-specific informed consent is signed. Must be obtained prior to performing any screening procedures.
Inclusion/Exclusion Criteria	X	
Demographics	X	
Medical History	X	Include any toxicities or allergies related to previous treatments. For Part B, all medical history relevant to MS should be obtained.
Safety Assessments		
Height, Weight, and BMI	X	BMI will be calculated.
Complete PE	X	If the Screening PE is performed within 24 hrs prior to tracer administration on Day 1, then a single complete PE is sufficient for both the Screening and Day 1 PE. See Section 9.4.1.
12-Lead ECG	X	ECGs should be recorded after the participant has been supine for at least 5 min. If the Screening ECG is performed within 24 hrs prior to tracer administration on Day 1, then a single ECG is sufficient for both the Screening and Day 1 ECG. See Section 9.4.5.
Vital Signs	X	VS (including body temperature, respiration rate, seated BP, and HR) should be measured after the participant has been resting quietly in a supine position for at least 5 min. See Section 9.4.3.
Allen's Test	X	Parts A and B only. Normal result must be documented in at least 1 arm.
C-SSRS	X	Part C only. Screening/baseline version with lifetime and 6 months review interval.
SAE Assessment	X	All SAEs must be collected from the time of signing the consent until 10 days after the last tracer administration or the final visit, whichever is later.

Table 2-1: Screening Procedural Outline for Parts A, B, and C (IM038010)

Procedure	Screening Visit(s) (Day -30 to Day -1)	Notes
		All AEs (SAEs and non-serious AEs) associated with SARS-CoV-2 infection must be collected from the date of participant's written consent. See Section 9.2.1.
Prior and Concomitant Medication Use	X	Includes prescription, over-the-counter medications, and herbal supplements. See Section 7.7.1 for Prohibited and/or Restricted Treatments.
Laboratory Tests		

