- In the case of prior SARS-CoV-2 infection, symptoms must have completely resolved and, based on investigator assessment, there are no sequelae (eg, shortness of breath, persistent cough, excessive fatigue, loss of smell) that would place the participant at a higher risk of receiving investigational treatment
- m) Positive test result for the presence of SARS-CoV-2 virus (eg, polymerase chain reaction [PCR] test) within 14 days of Day 1
- n) Any recent infection requiring antibiotic treatment within 4 weeks of Day 1
- o) Active herpes infection, including herpes simplex 1 and 2 and herpes zoster
- p) Known active malaria
- q) History or any evidence of active infection or febrile illness within 7 days of tracer administration (eg, bronchopulmonary, urinary, or gastrointestinal)
- r) Donation of blood to a blood bank or to another clinical study within 4 weeks of tracer administration (within 2 weeks for plasma only)
- s) Inability to be venipunctured and/or tolerate venous access
- t) Have any contraindication to arterial line insertion, including but not limited to, an abnormal Allen's test result, coagulation profile, allergy to local anesthetics, or other medical history or examination findings that in the opinion of the Investigator would make radial artery cannulation contraindicated (international normalized ratio [INR]/partial thromboplastin time [PTT]) at Screening (Part A and Part B)
- u) Contraindications against MRI imaging, including non-MRI compatible metal implants, cardiac pacemakers, cochlear implants, ventricular shunt systems; metal particles in the body that pose a risk to the participant, including large tattoos in regions affected by cranial MRI scanning and severe claustrophobia. Contraindications against gadolinium-based contrast agents including known hypersensitivity to gadolinium-based contrast agents (Part B only).
- v) Recent (within 6 months of study intervention administration) drug or alcohol abuse as defined in Diagnostic and Statistical Manual of Mental Disorders Fifth Edition (DSM 5), Diagnostic Criteria for Drug and Alcohol Abuse

w) Use of any tobacco- or nicotine-containing products (including but not limited to cigarettes, pipes, cigars, electronic cigarettes, chewing tobacco, nicotine patches, nicotine lozenges, or nicotine gum) within 3 months prior to the first dose of tracer administration (Part A and Part C)

- x) Any other sound medical, psychiatric, and/or social reason as determined by the investigator.

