9.2.1 Time Period and Frequency for Collecting AE and SAE Information

All SAEs must be collected from the time of signing the consent, including those thought to be associated with protocol-specified procedures, and within 10 days following discontinuation of dosing in Parts A and B, and within 28 days following discontinuation of dosing in Part C.

The investigator must report any SAE that occurs after these time periods and that is believed to be related to study intervention or protocol-specified procedure (eg, a follow-up skin biopsy).

- Medical occurrences that begin before the start of study intervention but after obtaining informed consent will be recorded on the appropriate section of the CRF module.
- All SAEs will be recorded and reported to Sponsor or designee within 24 hours, as indicated in Appendix 3.
- The investigator will submit any updated SAE data to the sponsor or designee within 24 hours of updated information being available.

Investigators are not obligated to actively seek AEs or SAEs in former study participants. However, if the investigator learns of any SAE, including a death, at any time after a participant has been discharged from the study, and he/she considers the event reasonably related to the study intervention or study participation, the investigator must promptly notify the Sponsor.

The method of evaluating and assessing causality of AEs and SAEs and the procedures for completing and reporting/transmitting SAE reports are provided in Appendix 3.

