#### 7.6.2 Adverse Events

All AEs will be coded and grouped into Preferred Terms (PT) by System Organ Class (SOC), using the current version of the Medical Dictionary for Regulatory Activities (MedDRA).

Treatment-emergent adverse events (TEAEs) will be defined as any AEs that start on or after administration of study treatment and until 10 days after last dose of study treatment or date of last study visit, whichever is later.

Only TEAEs will be tabulated. Events will be assigned to the study treatment administered to the participant. For tabulating incidence of TEAEs, the proportion of participants having an TEAE will be calculated as the number of participants experiencing the event, divided by the total number of participants in the Safety population. TEAEs will be summarized by SOC, PT, treatment, and overall.

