## 8.2.2 Incomplete Stop Date

If the imputed stop date is before the start date, then the imputed stop date will be equal to the start date.

Missing day and month:

• If the year of the incomplete stop date is the **same** as the year of the last dosing date, then the day and month of the last dosing date will be assigned to the missing fields.

- If the year of the incomplete stop date is **prior to** the year of the last dosing date or prior to the year of the first dosing date, then December 31 will be assigned to the missing fields.
- If the year of the incomplete stop date is **prior to** the year of the last dosing date but is the same as the year of the first dosing date, then the first dosing date will be assigned to the missing date.
- If the year of the incomplete stop date is **after** the year of the last dosing date, then January 1 will be assigned to the missing fields.

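### SAP 8.2.1 lets an AE known to have ended before first dosing be tabulated as treatment-emergent, because the known stop date is used in only one of its three missing-start-date cases

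*SAP*

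**What the plan says.** SAP 7.6.2 defines treatment-emergent adverse events (TEAEs) as "any AEs that start on or after administration of study treatment", up to a later cut-off, and tabulates only those. SAP 8.2.1 then handles incomplete start dates in three cases:

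- **Day and month missing.** If the year is that of first dosing, "then the day and month of the first dosing date will be assigned to the missing fields". Earlier years go to 31 December and later years to 1 January. No rule in this case refers to the stop date.
- **Day only missing.** A start in the month of first dosing is set to the first dosing date. The last bullet deals with events whose end is known: when "the imputed start date is after the stop date, the start date will be imputed by the stop date".
- **Day, month and year missing.** "No imputation is needed, the corresponding AE will be included as TEAE".

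SAP 8.2.2, on incomplete stop dates, places its own consistency rule ahead of all its cases: "If the imputed stop date is before the start date, then the imputed stop date will be equal to the start date".

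Pre-dose events do reach the database. Protocol Table 2-1 requires SAEs from consent, and also says "All AEs (SAEs and non-serious AEs) associated with SARS-CoV-2 infection must be collected from the date" of written consent. Protocol 9.2.1 adds "Medical occurrences that begin before the start of study intervention but after obtaining informed consent will be recorded" in the CRF.

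**The concern.** A stop date before first dose settles the timing of an event, however little is known about its start. The SAP accepts this when only the day is missing and ignores it in the other two cases. The same pre-dose event is therefore excluded or counted according to how much of its start date was lost. The year-only case also produces a record whose start falls after its stop.

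The first primary endpoint is the incidence, severity, seriousness and type of AEs, and Protocol Table 10.4.2-1 gives its timeframe as treatment-emergent. With at most 8 participants in each of Parts A and B, one wrong classification is visible in the table.

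**Working it through.** The plan gives no figure to reproduce, so the check applies the rules as written.

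**Worked example** (illustrative dates). First dose 28 June 2022 = Day 1. Known stop 20 June 2022 = Day -8, since SAP 6.1 has no Day 0. An event is treatment-emergent if its start is on or after 28 June.

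| Recorded start | Rule in SAP 8.2.1 | Resulting start | TEAE? |
|---|---|---|---|
| June 2022, day missing | Set to 28 June; later than the stop, so replaced by it | 20 June | No |
| 2022 only | Set to 28 June; no check | 28 June, 8 days after the stop (28 - 20) | Yes |
| Wholly missing | Counted by default | None | Yes |

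**Does SAP 8.2.2 repair this?** No. It changes only an imputed stop date, never the start date or TEAE status. Take a start of 2022 only and a stop of May 2022, with all dosing in June:

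1. SAP 8.2.1 sets the start to 28 June.
2. SAP 8.2.2 sets the stop to 31 May, the last day of a month other than the last-dosing month.
3. Its opening rule finds 31 May before 28 June and moves the stop to 28 June.

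The evidence that the event was over before dosing is overwritten.

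**Enumeration.** The 8.2.1 rules were run on every start from 1 to 30 days before dosing (the screening window), paired with every full stop date from the start to the day before dosing: 1 + 2 + ... + 30 = 465 pairs. Two first-dosing dates were assumed, one mid-year and one with screening crossing the year end.

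| Start date missing | Called TEAE, first dose 15 June 2022 | Called TEAE, first dose 10 January 2022 |
|---|---|---|
| Day only | 0/465 | 0/465 |
| Day and month | 465/465 | 45/465 |
| All | 465/465 | 465/465 |

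The 45 are the pairs that start in January (1 + 2 + ... + 9). The others start in the previous year, go to 31 December and are correctly excluded. So the day-and-month case fails only when the partial year is the dosing year. These counts show how the rules behave; they do not estimate how often such records arise.

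With the stop date used in all three cases, every cell becomes 0/465. All 165 simulated true TEAEs (11 start days from 0 to 10 after dosing, times 15 durations from 0 to 14 days) were kept.

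**Effect on incidence.** One misclassified participant adds at most 1/8 = 12.5 points in a part of 8, 1/6 = 16.7 points if Part A stays at 6, and 1/16 = 6.25 points in Parts A and B combined. Overall incidence does not change if that participant already has a TEAE, though system organ class or preferred term rows may.

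**The case against.** The strongest reply is that this will rarely matter. It needs a pre-dose event recorded as an AE in someone later dosed, a start date lacking at least its month, and a stop known to be pre-dose. Screening lasts about 30 days, SAEs are reported within 24 hours, and the exclusions for a recent positive SARS-CoV-2 test or recent infection narrow the field further. Protocol 9.2.1 sends other pre-dose occurrences to the appropriate CRF section without saying that it is the AE page. All of that stands, and it bears on frequency. It does not close the route: for SARS-CoV-2 the protocol requires that "In the case of prior SARS-CoV-2 infection, symptoms must have completely resolved", so such an event in a dosed participant should carry a pre-dose stop date.

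A second reply is that the stop-date bullet was probably meant to be general. That may be so, but it sits under one case, whereas SAP 8.2.2 puts its rule ahead of all its cases. Even read generally, it acts on an imputed start date, and in the wholly missing case nothing is imputed.

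A third is that counting events with unknown starts is a conservative default. That is sound when the timing is unknown; here the stop date makes it known.

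Fourth, SAP 8.2.2 does not say whether its start date includes an imputed one, and TEAE status does not depend on the stop date. Both are fair: the May example assumes that imputed starts are included, and it shows lost evidence rather than a further miscount.

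Finally, the analysis is descriptive, for a synoptic report, and all recorded AEs are listed, so an odd record could be noticed. That limits the harm but does not correct the table.

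**Conclusion.** The concern holds. Two of the three missing-start-date cases make no use of a known stop date. One fails whenever the partial year is the dosing year; the other fails for every event that ended before dosing. Both give a classification that conflicts with SAP 7.6.2, and no other rule corrects it.

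The error can only inflate TEAE counts; it hides no harm. Its practical size is probably small, and may be nil if no such record exists. The percentage bounds assume the maximum sizes of 8 per part (or 6 in Part A); actual denominators may differ because enrolment is capped rather than fixed and participants may be replaced. It should still be corrected, because a stated rule misclassifies events for a primary safety endpoint.

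**What to change.** In SAP 8.2.1:

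1. Move the stop-date check ahead of the three cases, so that it applies to any imputed start date.
2. Add that an AE whose stop date is before first dose is not a TEAE, including when the start date is wholly missing. The first change cannot reach that case, because no start is imputed there.
3. Apply this before SAP 8.2.2, and treat a partial stop date as pre-dose when its latest possible date is before first dose.
4. State a convention for a stop on the day of first dose; for example, the event stays a TEAE unless recorded times show that it ended before dosing.

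Excluded events remain in the listing of all recorded AEs for the Enrolled population, so nothing is lost from view.

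The core change is one or two sentences, with a short line for the dosing-day convention, plus the matching derivation code. No new data are needed. Events with no usable stop date are still handled as now, and in the enumeration no true TEAE was lost.

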## 8.2.2 Incomplete Stop Date

If the imputed stop date is before the start date, then the imputed stop date will be equal to the start date.

Missing day and month:

• If the year of the incomplete stop date is the **same** as the year of the last dosing date, then the day and month of the last dosing date will be assigned to the missing fields.

- If the year of the incomplete stop date is **prior to** the year of the last dosing date or prior to the year of the first dosing date, then December 31 will be assigned to the missing fields.
- If the year of the incomplete stop date is **prior to** the year of the last dosing date but is the same as the year of the first dosing date, then the first dosing date will be assigned to the missing date.
- If the year of the incomplete stop date is **after** the year of the last dosing date, then January 1 will be assigned to the missing fields.

#### Missing day only:

- If the month and year of the incomplete stop date are the **same** as the month and year of the last dosing date, then the day of the last dosing date will be assigned to the missing day.
- If either the year of the partial date is **not equal to** the year of the last dosing date or the years of the partial date and the last dosing date are the same but the month of partial date is **not equal to** the month of the last dosing date, then the last day of the month will be assigned to the missing day.

#### 9 CONTENT OF REPORTS

Statistical components for the clinical study report will be based on the content of this statistical analysis plan (SAP). Details of the tables, listings, and figures, as appropriate, to be prepared for the final synoptic CSR will be included in a study-specific Data Presentation Plan (DPP).

# 10 CHANGES TO THE STATISTICAL ANALYSES SECTION OF THE PROTOCOL

The statistical analysis of the secondary imaging endpoint will be carried out for the Response-Evaluable 2 population. The protocol erroneously refers to the Response-Evaluable 1 population here, however, this subset would apply to endpoints based on whole body scan data, not cranial scan data.

#### 11 DOCUMENT HISTORY

**Table 11-1: Document History** 

Version Number	Author(s)	Description
1.0		Original Issue

# APPENDIX 1 ABBREVIATIONS

**Table 11-2:** List of Abbreviations

Tuble II 2.	List of Abbit Autions
Abbreviation	Description
AE	Adverse Event
ATC	Anatomical Therapeutic Chemical
BMI	Body Mass Index
BMS	Bristol Myers Squibb
BTK	Bruton's Tyrosine Kinase
CNS	Central Nervous System
CRF	Case Report Form
CRU	Clinical Research Unit
CSR	Clinical Study Report
CT	Computed Tomography
%CV	Coefficient of Variation
DPP	Data Presentation Plan
ECG	Electrocardiogram
EDC	Electronic Data Capture
GdE	Gadolinium Enhancing
GLP	Good Laboratory Practices
ICH	International Conference on Harmonization
IND	Investigational New Drug
IV	Intravenous
MedDRA	Medical Dictionary for Regulatory Activities
MRI	Magnetic Resonance Imaging
MS	Multiple Sclerosis
NCI-CTC	National Cancer Institute - Common Terminology Criteria
PDAP	Protocol Deviation Assessment Plan
PET	Positron Emission Tomography
PT	Preferred Term
ROI	Region of Interest
SAE	Serious Adverse Event
SAP	Statistical Analysis Plan
SD	Standard Deviation

**Table 11-2:** List of Abbreviations

Abbreviation	Description
SE	Standard Error
SI	International System of Units
SOC	System Organ Class
SUV	Standardized Uptake Value
TEAE	Treatment-Emergent Adverse Event
VS	Vital Signs
$V_{T}$	Volume of Distribution
WHO-DD	World Health Organization's Drug Dictionary
